5.3.3. Data Analysis

Semi-structured interview

Interviews will be audio-recorded and transcribed verbatim.

Data analysis will be conducted by two researchers with experience in qualitative research. Interviews' transcriptions and free text from qualitative survey will be analyzed using thematic analysis [Braun 2006], whose analytical stages can be summarized as follows:

- Each researcher will read the transcriptions and write comments and initial thoughts in a memo.

Evaluating a Clinical Ethics Committee (CEC) implementation process in an Oncologic Research Hospital. A process evaluation study using Normalization Process Theory .

- Each researcher will extract portions of the text individually and then share their work to reach an initial agreement. During this stage, they will conduct the thematic analysis inductively [Braun V 2006] providing their insights.
- Researchers will independently review themes and allocate portions of the text to the newly reconfigured themes.
- Together, they will re-define themes and re-name them to achieve internal consistency.
- One researcher will extract from the interviews and draft the final report, which will be checked and amended by the other two.

The methodological rigor of the analysis will be further guaranteed by the supervision of a third, independent researcher.

After a first, inductive analysis of qualitative data, the construct of NPT will be applied to the emerging themes to interrogate, challenge, confirm or refine the themes. (McNaughton 2020).

Cognitive survey

The quantitative data collected by cognitive survey will be represented using descriptive techniques; that is, they will be summarized in terms of frequency and percentages for categorical variables, mean and standard deviation for symmetric quantitative variables and median and IQR for the remaining ones.

Free text from surveys will be analysed by thematic analysis described.

The study will be developed within 10 months since the CE AVEN approval.

6. ETHICAL CONSIDERATION

This clinical study was designed and shall be implemented and reported in accordance with the ICH Harmonized Guidelines for GCP, with applicable local regulations, and with the ethical principles laid down in the Declaration of Helsinki.

6.1 Ethics Committee Approval

The protocol, Subject Information Sheet, Informed Consent Form will be approved by the Ethics Committee (CE AVEN), as required in chapter 3 of the ICH E6 Guideline.

6.2 Subject Information and Informed Consent

Eligible subjects may only be included in the study after providing written (witnessed, where required by law or regulation), EC-approved informed consent. Informed consent must be obtained before conducting any study-specific procedures (i.e. all of the procedures described in the protocol). No study procedure can be performed before the written informed consent has been provided.

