The opinions/perspectives on the process implementation of the CEC from users and providers health professionals in terms of barriers/facilitators, expectations and needs will be assessed by using qualitative methods with large samples of participants from all staffs types and grades who were involved in designing, promoting, delivering and benefitting the CEC. Specifically, we will:

- a) interview Managers/Heads who formally supported and promoted the intervention
- b) interview CEC's members who delivered the intervention

Evaluating a Clinical Ethics Committee (CEC) implementation process in an Oncologic Research Hospital. A process evaluation study using Normalization Process Theory .

- c) interview HPs who benefitted the intervention by ethics consultation
- d) perform a cognitive anonymous survey targeting all the HPs who benefitted the intervention by attending the training course promoted by the CEC

Population

The qualitative evaluation is targeting to HPs (physicians, therapists, nurses, social workers) employed by the Local Health Authority of Reggio Emilia, and specifically to:

- Local Managers/Heads of Departments who have been contacted during the dissemination process
- CEC's member
- HPs who submitted an ethics consultation request,
- HPs who attended the training on ethics consultation provided by CEC;

Participant eligibility

Participants will be included if they:

- are working as a Head of Departments / local Manager at the Local health company of Reggio Emilia, who have been contacted by the CEC's president during the dissemination process
- have been a member of the CEC in the last 16 months;
- submitted at least 1 ethics consultation request;
- participated to at least 1 of 5 training courses on ethics consultation promoted by the CEC
- are HPs actually employed at the local Health Authority of Reggio Emilia
- Gave written consent

Recruitment Procedure (Interviews)

The center PI will contact by telephone or e-mail eligible participants, explaining the aims and procedures of the study and providing them with a document containing all the information related to the study's involvement (Attached 1). Participants expressing their interest in participation will be then contacted by telephone by the interviewer/facilitator who, after obtaining written informed consent to participate to the study (Attached 2) and to personal data treatment (Attached 3), will schedule an appointment for the interview.

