Personal interviews will be held via video teleconference (Lifesize system) or in presence, audio-recorded and transcribed in full.

Recruitment Procedure (cognitive survey)

All the HPs who registered to 1 of the 5 training course on ethics consultation will be recruited from the database of the Training Office. To guarantee HPs' anonymity, the PI will contact the Head of the Training Office who, on behalf of the PI, will sent an email to all the HPs attended the course. Since any further contact will be between the PI and the Head of the training office, it will not possible for the PI to identify who answer the survey. The email will contain all the information related to the study's objectives and a link to the online

Evaluating a Clinical Ethics Committee (CEC) implementation process in an Oncologic Research Hospital. A process evaluation study using Normalization Process Theory .

survey and it also specifies that any personal data will be required to fulfill the survey, which will be completely anonymous.

Participants are expected to submit the survey in two weeks from the first invitation. Then a reminder will be sent to submit responses within another week.

Data collection

Semi-structured interview

The semi-structured interview is a social interaction between two subjects: the interviewer and the interviewee. It has a cognitive purpose with the primary purpose of collecting data. The semi-structured interview guide includes a series of questions that must be asked to all interviewees without the need for a pre-established order, leaving space for any further investigation.

It will be the interviewer's concern to create a climate based on non-judgmental listening and mutual trust (Bichi 2007, Cocci 2005).

Therefore, the interviews will be conducted by the members of the research team, who have received special training in this regard and the place of the interview will be by the selected participating members.

The expected duration of the interview is between 30 and 50 minutes; the interview will be audio-recorded.

Interview's topic guide are informed by NPT four concepts.

Table 3: topic of Interviews' topic guide accordingly with NPT core concepts

concept	Key attribute	Topics of the interview are:
Coherence	Sense-making	motivations/ expectations to implement the CEC and understanding of its role within the Health Care Facility
Cognitive participation	engagement	understanding of personal commitment to the service

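### Does the written-consent rule in Section 6.2 shut out the respondents to the two anonymous surveys?

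*Combined protocol and SAP*

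**What the plan says.** Section 6.2 (Subject Information and Informed Consent) has three sentences. The first sets the condition for entry: "Eligible subjects may only be included in the study after providing written (witnessed, where required by law or regulation), EC-approved informed consent". The second requires consent before any study-specific procedure, glossed as "all of the procedures described in the protocol". The third repeats the rule: "No study procedure can be performed before the written informed consent has been provided".

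In Section 3, under Qualitative evaluation, Participant eligibility has six entries. Four name groups: managers and department heads, CEC members, staff who requested an ethics consultation, and those who "participated to at least 1 of 5 training courses on ethics consultation promoted by the CEC". The other two are current employment at the health authority and "Gave written consent".

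Recruitment is then described separately. For interviews, an appointment is made "after obtaining written informed consent to participate to the study (Attached 2" and a second attachment on data treatment. For training attendees the instrument is a "cognitive anonymous survey targeting all the HPs who benefitted the intervention by attending the training course". The Training Office emails the link so that "it will not possible for the PI to identify who answer the survey". The all-staff survey, under Quantitative evaluation, is also an anonymous emailed link, and its only eligibility condition is employment.

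**The concern.** Section 6.2 makes no exception, and both surveys are procedures that the protocol describes. Training attendees also appear in the list that ends with written consent. A strict reader would conclude that nobody recruited through the Training Office email satisfies the consent entry. The team would then have to depart from its own rule or collect signatures by a route the plan does not give.

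The training survey is the only source of NoMAD data, the study's one quantitative measure built on Normalization Process Theory. If its respondents were ineligible, that component would be lost. Section 6.3 adds to the unease: it asks for a log of names and signed forms, with no carve-out for people whom nobody can identify.

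**Working it through.** No arithmetic in the plan depends on this point: it gives no sample size, power or error rate. The check is a comparison of the texts.

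**1. Can the eligibility list be read literally?** It has 4 group entries + 2 conditions = 6 entries under one stem, with nothing to show which are alternatives. Taken as joint conditions, they admit only someone who is at once a manager, a CEC member, a consultation requester and a course attendee. That is plainly not meant. Treating the four groups as alternatives and the last two entries as common to all does not work cleanly either. The Composition paragraph gives 15 CEC members, 9 internal and 6 external, so the employment entry would bar 6/15 = 40% of the members whom the study intends to interview. The list is a loose inventory whose entries apply where they make sense, and the consent entry names no group.

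**2. Where is written consent put into practice?**

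| Component | Recruitment text | Signed form described |
|---|---|---|
| Interviews (three groups) | Recruitment Procedure (Interviews) | Yes, two attachments |
| Training-course survey | Recruitment Procedure (cognitive survey) | No; information email and link |
| All-staff survey | Quantitative evaluation, Recruitment Procedure | No; information email and link |

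The archiving of consents is described in the interview section, next to the transcripts. The specific procedures agree with one another: signatures for interviews, information plus a link for surveys. Section 6.2 reads as general good-clinical-practice text; its mention of witnessed consent has no evident use in a staff survey.

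**3. Is anonymity incompatible with consent?** No. The plan says that the investigator cannot tell who answered. A consent record kept apart from the answers would respect that. The text supports the statement that no step is described, which is weaker than saying that none is possible. Consent pages were also removed from the text under review, so survey wording may exist there.

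**4. What could change in the results?** Anonymous answers carry no identifier, so no response can be matched to a form and none can be dropped selectively for lack of one. The analyst can use all returned questionnaires or none. Using none would abandon a planned component, so the analysis set is all returned questionnaires. The summaries (frequencies and percentages, mean and SD or median and IQR, and thematic analysis of free text) are then the same whichever way the wording is read.

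**The case for a change.** The strongest reply is that intent is not text. Section 6.2 expressly reaches every procedure, and it does so even if the eligibility list is set aside. Nowhere does the protocol say that completing a survey counts as consent. Ethics committee approval under Section 6.1 does not settle the matter, because the approved document would contain both the general rule and the anonymous procedure. Removed attachments might supply a consent route, but they would not narrow the wording of Section 6.2. The study commits itself to good clinical practice and to inspection, and an inspector may fairly ask which rule governs the surveys.

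All of this stands as a comment on drafting: the scope of the rule is not stated. It does not establish that the respondents are ineligible. That conclusion requires reading the four group entries charitably and the consent entry to the letter, within the same list. Section 6.3 does not help either, since it is a confidentiality rule and excludes no data.

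**Conclusion.** The inconsistency in wording is real, but it calls for no change to the plan. Section 6.2 is broader than the procedures it governs. Those procedures show clearly enough that signed consent belongs to the interviews and that the surveys rest on an information email and voluntary completion. A team following the recruitment sections would run the study in the same way whether or not Section 6.2 were narrowed. The effect on estimates, precision, bias and descriptive conclusions is nil.

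This rests on two assumptions. First, the specific recruitment text takes precedence over the general ethics paragraph. Second, the ethics committee accepts a consent route for the surveys that needs no signature linked to the answers. If the committee required signed forms from survey respondents, fewer might reply. The documents give no figure from which to size that, and it would follow from the committee's decision, with the statistical plan unaltered. The scope of the rule can be clarified in the ordinary course of that submission.

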6.3 Confidentiality

The investigator must ensure participant anonymity. On database and other documents, participants must not be identified by name but by participant number and a code. The investigator must keep a separate log of

Evaluating a Clinical Ethics Committee (CEC) implementation process in an Oncologic Research Hospital. A process evaluation study using Normalization Process Theory .

'participants' codes, names and addresses, and signed informed consent forms, all of which must be kept strictly confidential.

Data generated by this study must be available for inspection upon request by representatives of the national and local health authorities, monitors, representatives, and collaborators, and the EC for each study site, as appropriate.

Appendix 1 Interview's topic guide

Coherence of the CEC	What is the process?	how participants who benefitted from CEC's activities perceive the CEC and whether they experienced the CEC as valuable to them and agreed about its usefulness and purpose.
Cognitive participation	Who performs the process?	whether participants saw the CEC as a legitimate part of their work and whether they supported it over time
Collective action	(How is the process performed?)	how the CEC was provided within the existing context, how the embedding and integration had proceeded, and what factors promoted or inhibited the work
Reflexive monitoring	(How is the process understood?)	how participants individually and collectively evaluate the CEC

The semi-structured interview with the Managers/Department Heads who promoted the intervention will reflect the following themes:

- A. Perception of the role of CEC in the local context, and motivations behind the implementation of CEC.
- B. Understanding of their own activities in support of CEC.
- C. Understanding the strengths and critical aspects related to the service
- D. Reflection on their perceived impact in the local context

Opening

Good morning, thank you for the time you dedicated to participate in this study. Regarding the purpose of the research, do you have any questions or concerns to clarify? Is it clear to you why we are here?

-Would you like to tell me what was your experience with Clinical Ethics Committee (CEC)?

Topic A - coherence :

-In your opinion, what is the role of the CEC within the Local healthcare Authority?

-How, in your opinion, is it different from other services and what is its specificity?

-What is the goal of the CEC and how does it act in the local context?

-Are there any motivations that prompted you to support/promote this service?

Evaluating a Clinical Ethics Committee (CEC) implementation process in an Oncologic Research Hospital. A process evaluation study using Normalization Process Theory .

Theme B - cognitive participation

-How do you help promote to this service?

-What do you think about the value of a service like CEC to your work and your colleagues?

Topic C - collective action

-Thinking about the activities carried out by the CEC, how have they been integrated into the local context?

-Were there any limitations (organizational? Internal? External to the service? Economic?) that you perceive with respect to the CEC? If yes, which ones?

-Were there potentials instead with respect to the service that was implemented? If yes, which ones?

Topic D - reflexive monitoring

-Considering what has been done in these 16 months, how do you evaluate the service?

- In what ways could the CEC be improved?

Conclusion

Do you have any additional thoughts, examples, comments to share?

Evaluating a Clinical Ethics Committee (CEC) implementation process in an Oncologic Research Hospital. A process evaluation study using Normalization Process Theory .

The semi-structured interview with CEC's members will reflect on the following themes:

- A. Perception of the CEC's role in the local context and motivations for participating in it
- B. Understanding of their own activities in support of the CEC
- C. Understanding of strengths and critical issues related to the service
- D. Reflection on service use and perception of the impact produced in the local context

Opening

Good morning, thank you for your willingness to participate in this study. Regarding the purpose of the research, do you have any questions or concerns to clarify? Is it clear to you why we are here?

1. Would you like to tell me about your experience with the CEC?

Topic A - coherence

- In your opinion, what is the role of the CEC within the local Health Care Authority?
- How, in your opinion, is it different from other services and what is its specificity?
- What is the goal of the CEC and how does it act in the local context?
- What are your motivations for taking part in this service?

Theme B - cognitive participation.

- What does your work in this service consist of?
- What do you think about the value of a service like the CEC to your work and to your colleagues?

Theme C - collective action

- Thinking about the activities carried out by the CEC, how were they integrated into the local context?
- Were there any limitations (organizational? Internal? External to the service? Economic?) that you perceive with respect to the CEC? If yes, which ones?
- Were there strengths with respect to the service that was implemented? If yes, which ones?

Topic D - reflexive monitoring

- In light of what has been done in these 16 months, how do you evaluate the implemented service?
- In what ways could the CEC be improved?

Conclusion

Do you have any additional thoughts, examples, comments to share? Are there any important things that did not come up during the interview?

Evaluating a Clinical Ethics Committee (CEC) implementation process in an Oncologic Research Hospital. A process evaluation study using Normalization Process Theory .

The semi-structured interview with professionals who required an ethics consultation to the CEC will reflect on the following themes:

- A. Motivations and factors that prompted the request
- B. Evaluation of their own experience in terms of: perceived support, impact in their own Clinical case, impact on their daily experience;
- C. Evaluation of the CEC activity in terms of: access, satisfaction with the service; strength aspects, critical aspects related to counseling, clarity and comprehensibility of response, availability...
- D. Suggestions and overall opinion about the CEC.

Opening

Good morning, thank you for the time you dedicated to participate in this study. Regarding the purpose of the research, do you have any questions or concerns to clarify? Is it clear to you why we are here?

Topic A - coherence

- 1. Would you like to tell me how you came to know about CEC?
- 2. Would you like to tell me about the case that prompted you to contact the CEC?
- 3. What were the reasons that convinced you to ask for a support to the CEC?

Theme B - cognitive participation

- 1. With respect to the case you told me about, did you feel supported by CEC? If yes, how?
- 2. What impact did the CEC's advice have on the case?
- 3. What differences did you perceive in your daily clinical practice as a result of this case and the CEC's involvement?

Topic C - collective action

- 1. How do you rate your experience with the counseling service offered by the CEC? Was it easy to access?
- 2. What do you think are the strengths of this service?
- 3. What do you think are the critical aspects of this service?

Topic D - reflexive monitoring

- 1. What do you take home from this experience?
- 2. What is your overall assessment of the ECC?

Conclusion

Do you have any additional thoughts, examples, comments to share? Are there any important things that did not come up during the interview?

Evaluating a Clinical Ethics Committee (CEC) implementation process in an Oncologic Research Hospital. A process evaluation study using Normalization Process Theory .
Version 1, December 23, 2021

[figure not shown]
Appendix 2

Guide and Track of the survey to participants of the training course promoted by the Clinical Ethics Committee

This survey is designed to better understand how to apply and integrate complex interventions into daily clinical practices. Specifically, this survey asks questions about the implementation process of the Clinical Ethics Committee (CEC) at the Local Health Authority of Reggio Emilia.

The survey is composed by 2 parts. The first part contains a series of more detailed questions about the implemented intervention through closed-ended questions. The second, on the other hand, contains some open-ended questions concerning some aspects of this intervention. Please take the time to decide which answer best fits your experience for each statement and check the appropriate box.

This Survey was developed following the model of Finch, T.L., Girling, M., May, C.R., Mair, F.S., Murray, E., Treweek, S., Steen, IN, McColl, E.M., Dickinson, C., Rapley, T. (2015). Nomad: mplementation measure based on Normalization Process Theory. [Measurement instrument]. Accessed at: <http://www.normalizationprocess.org>.

[figure not shown]
**Evaluating a Clinical Ethics Committee (CEC) implementation process in an Oncologic Research Hospital. A process evaluation study using Normalization Process Theory .
Version 1, December 23, 2021**

n.	Question	Agree	Partially Agree	Neutral	Partially disagree	Disagree
1	I'm able to distinguish CEC from the usual hatreds of working					
2	Staff in this organization have a shared understanding of the purpose of CEC					
3	I understand how CEC affects the nature of my work					
4	I am able to see the potential value of CEC to my work					
5	There are managers in place to ensure the delivery of the intervention and to engage other practitioners					
6	I believe that participating in the dissemination of the CEC is a legitimate function of my role					
7	I am willing to work in new ways with my colleagues to use CEC					
8	Continuerò a supportare l'utilizzo del CEC					
9	I will continue to support the use of CEC					
10	Turning to CEC disrupts working relationships					
11	I have confidence in the ability of other practitioners to use CEC					
12	The work is assigned to professionals who possess adequate skills to use CEC					
13	Sufficient training has been provided to enable staff to implement CEC					
14	Sufficient resources are available to support the delivery of CEC					
15	Management adequately supports the delivery of the ECC					
16	I am aware of scientific reports on the effects of CEC					
17	Staff agree that using CEC is fruitful.					
18	I appreciate the effects the delivery of CEC has had on my work					

**Evaluating a Clinical Ethics Committee (CEC) implementation process in an Oncologic Research Hospital. A process evaluation study using Normalization Process Theory .
Version 1, December 23, 2021**

19	It is possible to use the feedback collected on the CEC to improve the tool in the future					
20	I can modify the way I work with the CEC					
A	In what ways can the CEC be improved??					
B	What aspects would you like CEC to address in the future?					
C	What has CEC brought to the health care facility where you work?					
D	Do you have additional opinions and/or suggestions with respect to the way this service operates?					

**SERVIZIO SANITARIO REGIONALE
EMILIA-ROMAGNA**
Azienda Unità Sanitaria Locale di Reggio Emilia
IRCCS Istituto in tecnologie avanzate e modelli assistenziali in oncologia

**Evaluating a Clinical Ethics Committee (CEC) implementation process in an Oncologic Research Hospital. A process evaluation study using Normalization Process Theory .
Version 1, December 23, 2021**

Normalization Measure Development Questionnaire (short NoMAD)

(Adapt the questionnaire to your purposes by specifying [the intervention] you are using inside the brackets)

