Evaluating a Clinical Ethics Committee (CEC) implementation process in an Oncologic Research Hospital. A process evaluation study using Normalization Process Theory .

interact within the wider context of the intervention, such as existing organizational structures and procedures [May 2018].

Table 1. NPT's 4 core concepts

concept	Key attribute	Working definition
Coherence	Sense-making	The extent to which individuals really understand all the elements of the intervention and the reasons for adopting it a new intervention
Cognitive participation	engagement	The extent to which individuals believe in the innovation provided by the intervention and start to prepare for it
Collective action	enacting	What happens when the intervention is operationalized
Reflexive monitoring	Appraisal	The act of keeping an innovation under review and adapting it intelligently to changing circumstances

NPT will be used as methodological framework to perform PE of the CEC implemented at the Local Health Authority of Reggio Emilia.

3. The evaluation study

PE of complex interventions usually requires a combination of basic quantitative measures of implementation with in-depth qualitative data to provide detailed understandings of intervention functioning on a small scale [Moore 2014].

Our referral framework is the mixed methods approach which, by integrating the quantitative findings with the qualitative findings, aims to provide a more comprehensive picture of the intervention than either method can do [Craig 2008].

I) Quantitative evaluation will include of CEC's activities performed within 16 months since its implementation and survey among all the HPs employed at the Local Health Authority of Reggio Emilia to understand the spread, use and knowledge of the service. These will be used to examine aspects of 'dose' (the quantity of intervention implemented); and the 'reach' of interventions (whether the intended audience comes into contact with the intervention, and how) (Moore 2015).

II) Qualitative methods (semi-structured interview and cognitive survey) will be used to investigate mechanisms of impact and contextual factors among several groups of stakeholders, differently involved in designing, promoting, delivering, and benefitting the intervention. We will use Normalization Process Theory to determine if, and in what ways, the CEC can be successfully 'normalized' (embedded) into clinical practice [Murray 2010, May 2018].

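### The interview guide for consultation requesters has no direct question on engagement, although its Theme B carries the cognitive participation label

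*Combined protocol and SAP*

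**What the plan says.** In section 3 (Materials and methods), under the semi-structured interview, the protocol states: "Interview's topic guide are informed by NPT four concepts". It describes cognitive participation in three places:

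- Table 1 (NPT core concepts), with engagement as the key attribute: "The extent to which individuals believe in the innovation provided by the intervention and start to prepare for it".
- Table 3 (interview topics by concept): "understanding of personal commitment to the service".
- The table at the head of Appendix 1: "whether participants saw the CEC as a legitimate part of their work and whether they supported it over time".

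Appendix 1 then gives a separate guide for each of three groups: managers and department heads, CEC members, and professionals who requested a consultation. The requester guide describes its theme B as "Evaluation of their own experience in terms of: perceived support, impact in their own Clinical case, impact on their daily experience". The three questions under the cognitive participation label follow that description: "With respect to the case you told me about, did you feel supported by CEC", "What impact did the CEC's advice have on the case" and "What differences did you perceive in your daily clinical practice as a result of this case and the CEC's involvement".

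Under Data Analysis (5.3.3), transcripts are first coded inductively, and the NPT constructs are then applied to the themes that emerge.

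**The concern.** The label and the content of Theme B do not match in this guide. All three descriptions of the concept concern what the participant brings: belief, commitment, a sense that the CEC belongs to the job, and continuing support. The requester questions concern what the participant received and what followed from it.

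The study wants to learn whether the CEC can become embedded in routine practice, and its background cites low referral rates and limited willingness to use such committees. Requesters are the interviewed group with direct experience of asking for a consultation. Whether they regard turning to the CEC as part of their role, and whether they would do so again, bears directly on that aim. If nobody asks, the material on engagement depends on what interviewees happen to volunteer.

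**Working it through.** No arithmetic beyond counting applies, and the protocol states no figure to reproduce. The check sets each numbered question of the requester guide against the three descriptions of the concept.

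**Theme B of the requester guide (3 questions)**

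1. Feeling supported by the CEC: support received.
2. Impact of the advice on the case: a perceived outcome.
3. Differences in daily practice: a perceived outcome.

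Questions asking directly about commitment, legitimacy or continued support: 0 of 3.

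**Rest of the requester guide (3 + 3 + 2 = 8 numbered questions)**

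- Topic A (3): how the requester came to know of the CEC, the case, and the reasons for asking. The third is the nearest to engagement, but it looks back at one request.
- Topic C (3): rating of the experience and ease of access, strengths, critical aspects.
- Topic D (2): what the requester takes away, and the overall assessment.

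Direct questions on the concept: 0 of 8, so 0 of 3 + 8 = 11 in the whole guide.

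**Comparison with the other two guides (2 Theme B questions each)**

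- Managers: the first asks how they help to promote the service, which is their own contribution. The second asks about the CEC's value to their work and colleagues.
- Members: the first asks what their work in the service consists of, again their own contribution. The second is the same value question.

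The Appendix 1 header places perceived value under coherence, so the value question is not counted as a clear match. That leaves at least 1 of 2 in each guide.

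**Cover elsewhere**

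The modified NoMAD survey in Appendix 2 asks about legitimacy (item 6), willingness to work in new ways (item 7) and continued support (item 9). It goes to people who attended the CEC's training. The Training Office sends the invitations, and the investigator cannot identify who answers. Some requesters may also have attended training, but their answers could not be picked out, so the survey does not fill the gap for requesters as a group.

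**The case against.** The strongest case on the other side is that the guides are deliberately tailored. The table of data sources gives requesters their own objective, exploring their experience of the consultation, and questions on support and impact serve it well. The interviews are semi-structured, with room to probe, and they close with an open invitation to add anything missed. The question on reasons for asking may draw out belief in the service, which Table 1 counts as part of the concept. Because NPT is applied to themes after inductive coding, the headings in the guide do not fix how answers are coded.

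Much of this stands, and it rules out several stronger readings that a reader might infer:

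- *That requesters will yield no evidence on engagement.* Probing, the question on reasons and the closing question could each produce some. Thin evidence is the supportable claim.
- *That a comparison of managers, members and users by NPT concept will fail.* The analysis section plans no such comparison.
- *That users as a whole are not asked.* Training attendees are also beneficiaries of the CEC, and their survey asks them.
- *That both Theme B questions in each of the other guides meet the definition.* Only one of two clearly does.
- *That the missing question on the CEC's role is a comparable defect.* The table of data sources assigns that topic to managers, members and training attendees. Table 3 also lists motivations under coherence, and requesters are asked about those.
- *That the impact questions must move to Topic C.* Table 3 puts perceived outcomes under collective action, but the other two guides list perceived impact under theme D, so their proper place is open.

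One part of the objection does not stand. Tailoring explains different wording, but here the content of the concept has been replaced while its label remains. Table 3 and the Appendix 1 header make no exception for requesters. The protocol also separates questions that every interviewee must be asked from further probing, which is left to the interviewer.

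**Conclusion.** The concern holds as a gap in the content of one of three interview guides. None of the 3 Theme B questions for requesters, and none of the guide's 11 numbered questions, asks directly about commitment, legitimacy or continued support. In each of the other two guides at least 1 of 2 Theme B questions addresses the participant's own contribution. The likely consequence is thin, unprompted evidence on this one NPT concept from the people who used the consultation service. A secondary risk is that answers about impact are read as engagement because they were collected under that heading.

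This rests on the protocol's own descriptions of the concept and on taking the questions as printed. It does not put the thematic analysis or the other data sources in doubt. It is a modest weakness that is cheap to correct before interviews begin.

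**What to change.** Keep the three support and impact questions, since they serve the objective set for requesters, but do not treat them as the cognitive participation prompts. Add one or two questions under Theme B: whether the requester regards turning to the CEC as properly belonging to their role, and whether they would turn to it again or encourage colleagues to do so.

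The guide would go from 11 numbered questions to 12 or 13, at a cost of a few minutes within the planned 30 to 50. Adding the CEC-role question used in the other guides, or moving the impact questions to another topic, is optional and not needed to close the gap.
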